## Methodology

#### Study design

It will be a Multicentre, Single blind, Randomized Controlled Trial.

The participant will be divided into three groups namely Group A (384 intervention group and 384 control group), Group B (20 patient) and Group C (10 healthy person).

**Group A** Number of participants 768 COVID-19 positive, moderately ill admitted patient who will receive intervention once (2 puff 0.6% PVP-I in each nostril and 2 puff inside mouth).

Step 1: Enrollment of the study populations by applying inclusion and exclusion criteria

Step 2: Randomization to allocate experimental and controlled group by using table of random number

Step 3: Application of 0.6% PVP-I spray to experimental group and distilled water to control group

Step 4: Follow up (waiting for 2-5 minutes)

Step 5: Collection of nasopharyngeal and oropharyngeal sawab for RT-PCR test for both group

Step 6: Observation of the patients for 30 minutes for possible early adverse effects (if any) and subsequent management (if needed).

Step 7: Analysis data collection, data processing and analysis by using SPSS software.

**Group B** Number of participants 20 asymptomatic to mild COVID -19 patients to whom after single time application of PVP-I oro-nasal spray, RT-PCR test will be done hourly for 4 hours in a single day (to assess the duration of effectiveness of PVP-I oronasal spray).

Step 1: Selection of 20 patients randomly with no or mild symptoms and obtain their consent for the further tests.

Step 2: Collection of 2nd, 3rd and 4th sample from nasopharynx and oropharynx hourly

Step 3: Data collection, data processing and analysis by using SPSS software

**Group C** Number of participants 10 healthy individual who accept intervention 0.6% PVP-I oronasal spray 3-4 hours interval but not more than 4 times a day for 30 days.

Step 1: Selection of 10 healthy volunteers randomly who will be selected for using 0.6% PVP-I Oro-Nasal spray 2 puff inside both nostrils and mouth 3 to 4 times a day for one month.

Step 2: Collection of blood & urine of participants on day 0, 10, 20, 30 for determination of any change in biochemical marker (thyroid, kidney and liver functions will be done)

Step 3: Data collection, data processing and analysis by using SPSS software

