#### 6. How Supplied

PONS\_aqueous solution containing 0.6%PVP-I is supplied in 30ml amber color High Density Poly Ethylene (HDPE) bottle designed for pharmaceutical packaging to provide adequate protection against sun light.

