#### N.B.

- Data collectors and Health Care Worker (HCW) involving in the research will be provided with standard and adequate number of all protective gears for their personal protection. Even though, if anyone become infected all the necessary treatment will be provided from the respective hospital without any expenditure.
- Viral concentration will be estimated semiquantitatively by analyzing the 'Cycle threshold value (CT value)' following RT- PCR. The CT value is a semiquantitative value that broadly categorises the concentration of viral genetic materials (NA) is in the samples. The CT value is inversely proportional to the concentration of viral genetic materials.i.e. low CT means high concentration of viral genetic materials and high CT value is the low concentration of viral genetic materials.
- BRiCM ensures Raw material & impurities characterization and determination of shelf life by performing the stability studies as follows:

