#### Stability Study & Shelf-life estimation

- Stability studies of the product are carried out at both accelerated condition as well as real time condition as per International Council for Harmonization (ICH) guidelines applicable for Stability Zone Iva.
- Stability studies at accelerated condition is carried out at 40 deg. C up to 12 months in 2 months interval and stability studies at real time condition is carried out at 25 deg. C up to two years in three months interval.
- Stability indicting parameters such as color of the solution, pH, available iodine, UV absorbance are included in both stability studies.
- Findings of both accelerated and real time stability studies are used to predict the shelf-life of the product up to two years.

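### The single-blind label does not say who is masked, and nothing masks the sprayer, the swab taker or the RT-PCR laboratory, leaving an avoidable risk of bias in the Ct comparison

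*Protocol*

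**What the plan says.** The Study design section of the Protocol states: "It will be a Multicentre, Single blind, Randomized Controlled Trial". It does not say which party is blinded. The sizes are "Group A (384 intervention group and 384 control group), Group B (20 patient) and Group C (10 healthy person".

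The Group A steps run in one session. Allocation comes from a table of random numbers, followed by "Application of 0.6% PVP-I spray to experimental group and distilled water to control group", then "Follow up (waiting for 2-5 minutes", then "Collection of nasopharyngeal and oropharyngeal sawab for RT-PCR test for both group". The N.B. that follows adds: "Viral concentration will be estimated semiquantitatively by analyzing the 'Cycle threshold value (CT value)' following RT- PCR".

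On supplies, section 6 (How Supplied) describes a "30ml amber color High Density Poly Ethylene (HDPE) bottle" for the active product. The N.B. under Selection Criteria says only that controls also receive a spray, of distilled water. No section describes a matching container, a coded label or how allocation is concealed. The stability section lists "Stability indicting parameters such as color of the solution", without stating the colour. Section 10 (Undesirable effects) mentions brief irritation or burning.

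The nearest text to masking is in Data Collection instrument and Technique, Subject Confidentiality, and Ethical Issues: subjects are identified by numbers and initials, and data are coded and analysed anonymously. That protects identity. It does not hide the arm. The SAP says nothing on blinding.

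**The concern.** RT-PCR is read by a machine, but what reaches the machine depends on how the swab is taken and when. That swabbing depends on the operator is general measurement knowledge; the documents do not say it. The wait may differ 2.5-fold between patients (5/2), and nothing requires it to be the same in both arms or to be recorded.

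If those who time and take the swab know the arm, small systematic differences in depth, vigour or timing would shift Ct in one direction. A larger sample does not dilute such a shift. It shrinks the standard error around it and makes it more likely to be declared significant.

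The setting makes this worth closing off. The Summary calls earlier data from this programme very satisfactory, and Utilization of Results plans to encourage public use of the spray for prevention. A spurious positive result would therefore have consequences outside the trial.

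**Working it through.** **1. The plan's own figure.** Sample Size (Protocol and SAP): n = Z²pq/d² = 1.96² × 0.5 × 0.5 / 0.05² = 384.16, so the stated 384 reproduces. This is the precision of a single proportion (±5 points). It contains no effect size and no power, so the sensitivity of the two-arm comparison has to be worked out separately.

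**2. Inputs for the comparison.** 384 per arm (Study design). Critical value 1.96, taken as a two-sided 5% test (Sample Size; 95% in the SAP). The documents give neither an SD for Ct nor any size of bias. Both are assumed here: SD 3 to 8 cycles, bias 0.5 or 1 cycle.

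**3. Precision on Ct.** SE = SD × √(2/384) = 0.0722 × SD. The smallest significant difference is 1.96 × 0.0722 × SD = 0.14 SD, whatever the SD.

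**4. Chance that pure bias b gives p<0.05 with no true effect:** Φ(b/SE − 1.96) + Φ(−b/SE − 1.96). For SD 5, SE = 0.361:
- b = 0.5: b/SE = 1.39, giving about 28%.
- b = 1: b/SE = 2.77, giving about 79%.

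| Assumed SD (cycles) | SE | Smallest significant difference | p<0.05 from 0.5-cycle bias | p<0.05 from 1-cycle bias |
|---|---|---|---|---|
| 3 | 0.217 | 0.42 | 64% | 99.6% |
| 4 | 0.289 | 0.57 | 41% | 93% |
| 5 | 0.361 | 0.71 | 28% | 79% |
| 6 | 0.433 | 0.85 | 21% | 64% |
| 7 | 0.505 | 0.99 | 17% | 51% |
| 8 | 0.577 | 1.13 | 14% | 41% |

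The nominal rate is 5%.

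**5. What such a bias would take.** If material doubles with each cycle (assumed), collecting a fraction f of the usual material shifts Ct by −log₂(f): 0.51 cycle for f = 0.7 and 1.0 cycle for f = 0.5. A 0.5-cycle bias thus means about 30% less material on average in one arm, and a 1-cycle bias means half.

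**6. If the outcome were PCR positive or negative.** The inclusion criteria require a positive RT-PCR within 24 hours, so positivity should be high. Assume 90%, with a pure bias to 85% in one arm. The pooled SE is √(2 × 0.875 × 0.125/384) = 0.0239, so a difference above 1.96 × 0.0239 = 0.0468 is significant. The unpooled SE is √((0.9 × 0.1 + 0.85 × 0.15)/384) = 0.0238. The chance of significance is Φ((0.05 − 0.0468)/0.0238), about 55%.

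**The case against.** **Staff may in fact be masked.** The documents never say that they know the arm, nor that one person reads the table, sprays and swabs. A reader might infer from the single-blind label that staff are aware. That is its usual meaning, but here it is inference from usage and silence. What stands is narrower: masking of outcome collection is not described.

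**Colour and burning are weak evidence.** A reader might infer that the product gives itself away by colour. The stability section lists colour as a parameter without stating it, and an amber bottle would tend to hide it, although no section says the control uses that bottle. Burning is felt by the patient, so it bears mainly on participant blinding.

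**The bias sizes are hypothetical.** A 1-cycle mean shift needs about half the material to be lost, in one direction, on average over 384 patients at three hospitals. This objection is fair: the percentages are conditional and do not estimate this trial's false-positive rate.

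**The hoped-for effect is far larger.** The Study Rationale cites a reduction of at least 4 log₁₀ for a gargle, which is 4/0.301 = 13.3 cycles if material doubles each cycle. Beside that, 0.5 to 1 cycle is small. But Endpoints sets no threshold for virucidal efficacy, so nothing in the plan stops a small significant difference from being read as success.

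**Separate swab takers cost something.** A second worker in close contact adds exposure, which the N.B. under Sponsoring agency itself treats as serious. This limits how firmly that part of the fix can be asked for.

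**Conclusion.** The point holds as a risk of bias that the plan leaves open. The masked party is not named, no section masks the sprayer, swab taker or laboratory, no coded or matching supplies are described, and the swab time may vary within a window without being recorded.

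The documents do not show that staff know the allocation or that any bias would occur. The link from the primary endpoint to Ct is itself drawn from the Group A steps and the N.B., because Endpoints names no scale.

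The size is illustrative: about 28% (0.5 cycle) and 79% (1 cycle) at SD 5, with ranges of 14% to 64% and 41% to 99.6% over SD 8 to 3. Even the mildest case shown is nearly three times the nominal 5%. A reader might also carry the sample-size value of p = 0.5 into a positivity comparison. That value is a placeholder for unknown prevalence and does not fit patients who were all RT-PCR positive at entry. The 90% figure used above is an assumption too, but better suited to them.

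This should be corrected because the remedy is cheap, not because the result is shown to be invalid.

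**What to change.** In Study design, under Methodology:

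1. Supply the active spray and the distilled water in identical amber bottles labelled only with a randomisation code, with the code list held away from those who spray and swab.
2. Send tubes to the RT-PCR laboratory with the subject number only (one that does not reveal the arm), and state that the laboratory is masked to arm.
3. Set one waiting time for both arms within the protocol's own 2 to 5 minute window, and record the actual time for each patient.
4. Name who is masked.
5. Where existing staff allow, have the swab taken by someone who did not apply the spray.

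The cost is labelling and a code list. No extra patients, visits or assays are needed. Laboratory masking is close to free, and a fixed waiting time limits one route of bias even if masking fails. The limitation is that colour, residue or burning may still unmask some participants and swab takers. The protocol should therefore claim swab-taker masking only as far as it is achieved.

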#### Place of study

Dhaka Medical College Hospital, Kurmitola General Hospital and Kuwait Moytree Hospital including product development & quality assurance will be held at Bangladesh Reference Institute for Chemical Measurements (BRiCM)

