## **Sampling Technique**

Random sampling procedure will be followed by using table of random numbers Admitted patients of dedicated Covid-19 hospital like KGH, KMH and DMCH will be taken after fulfilling of inclusion and exclusion criterias. Then from interested participants written informed consent will be taken. After ward randomization will be carried out to select intervention group and control group.

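### The plan does not say how the random sequence for three hospitals is generated, held, concealed or stratified, and no listed analysis includes hospital

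*Protocol*

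**What the plan says.** The Study design section of the protocol states: "It will be a Multicentre, Single blind, Randomized Controlled Trial". The blinded party is not named. The Place of study section lists three enrolling hospitals.

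Group A is planned as "Group A (384 intervention group and 384 control group", 768 patients in all. Its Step 2 gives the allocation method: "Randomization to allocate experimental and controlled group by using table of random number". Step 3 reads: "Application of 0.6% PVP-I spray to experimental group and distilled water to control group".

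The Sampling Technique section says "Random sampling procedure will be followed by using table of random numbers". It then places the eligibility check and written consent first, and continues: "After ward randomization will be carried out to select intervention group and control group".

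The Data Analysis section of the protocol and section 2 of the SAP list chi-square, t-test, F-test, ANOVA and correlation. Neither names a stratification factor, a covariate or a hospital term. The protocol promises an analysis plan, but the SAP supplied adds nothing on site. Under Data Collection instrument and Technique and under Subject Confidentiality, subjects are identified by a site number among other items, so the variable will exist.

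**The concern.** Random allocation protects the comparison only if the person deciding whom to enrol cannot know the next assignment. The documents name a source of random numbers but describe no barrier between the sequence and the enrolling staff.

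This matters more here for three reasons.

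- The trial is single blind, and no matching of the two sprays is described. The control is distilled water, while the colour of the active solution is one of its stability parameters. Staff may therefore recognise the arms.
- Entry requires a recent positive RT-PCR, so information on viral load may be at hand when patients are enrolled.
- The Group A steps list one swab, after the spray. With no pre-spray swab in those steps and no baseline Ct adjustment planned, steering by viral load could go unnoticed.

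The second issue is precision. If Ct differs between hospitals, through case mix, sampling or laboratory, an analysis without hospital carries that variation as noise. Unstratified allocation also allows the arms to differ by chance in their hospital mix.

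**Working it through.** **The plan's own figure.** With Z = 1.96, p = q = 0.5 and d = 0.05 (protocol, Sample Size; SAP section 1), n = Z²pq/d² = 3.8416 × 0.25 / 0.0025 = 384.16. The stated 384 per arm reproduces, and 2 × 384 = 768. The formula is for the precision of one proportion, so the documents give no power for the two-arm comparison. The power figures below rest on an assumed effect.

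**What the documents settle about allocation**

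| Item | Stated? |
|---|---|
| Source of random numbers | Yes, a table |
| Order | Yes, after eligibility and consent |
| Who generates and holds the sequence | No |
| Concealment until assignment | No |
| Simple, blocked or fixed-total | No |
| Stratified by hospital | No |

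**What poor concealment could do (illustration, all inputs assumed).** Suppose a fraction f of each arm is steered, and patients steered to the two arms differ by 1 SD of Ct.

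- Bias = f × 1 SD, so f = 5%, 10% or 20% gives 0.05, 0.10 or 0.20 SD.
- Standard error with 384 per arm = √(2/384) = 0.072 SD.
- The test statistic shifts by about 0.69, 1.39 or 2.77. The two-sided false-positive rate becomes about 11%, 28% or 79% instead of 5%.

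**Guessing without sight of the list.** The guesser is assumed to know all past allocations and to name the arm that is behind. Simulated correct guesses are 50% under simple randomisation, 52% if exactly 384 of 768 are drawn, and 71% with fixed blocks of 4. With sight of the list it is 100% under any scheme. The weak point is therefore concealment, and fixed small blocks would make guessing easier.

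**Leaving out hospital.** Assume three hospitals of 256 with equally spaced mean Ct, gap g, and within-hospital SD s. Between-hospital variance is 2g²/3, and the standard error inflates by √(1 + (2g²/3)/s²).

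- g = 2, s = 5: 2.67/25 = 0.107, and √1.107 = 1.05.
- g = 3, s = 5: 6/25 = 0.24, and √1.24 = 1.11.

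A wider range, with g in units of s and an assumed effect of 0.2024 s (80.1% power with hospital adjusted for):

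| g/s | Power without hospital | Loss (points) | SD of chance bias (units of s) |
|---|---|---|---|
| 0.25 | 78.5% | 1.6 | 0.015 |
| 0.5 | 73.8% | 6.3 | 0.030 |
| 1.0 | 58.4% | 21.7 | 0.059 |

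In 4,000 simulated trials per row under simple randomisation, mean bias was about zero and type I error was 5.1% to 5.3%. The cost is precision and chance imbalance, with no systematic bias.

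**The case against.** The strongest reply is that silence is not a flaw in the method. A random-number table can produce a simple, blocked, stratified or fixed-total list, and no passage says that enrolling staff can see it. The order of events is already right, because consent and eligibility come first. ANOVA and the F-test are listed and could carry a hospital factor, and an analysis plan is promised.

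Much of this stands. A reader might infer that the list is open, unblocked and unstratified and that staff will foresee allocations. The documents do not say so. They support only the statement that no safeguard is described. Consent before randomisation helps, but does not stop a person who knows the next assignment from choosing whom to approach. ANOVA could include hospital, but the SAP as supplied does not plan it.

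A reader might also infer that missing the exact 384/384 split is a defect. Under simple randomisation of 768, the chance of an exact split is C(768,384)/2^768 = 2.9%, and the 95% range for one arm is 357 to 411. Yet at 411/357 the efficiency is 4 × 411 × 357 / 768² = 99.5%, and power at the assumed effect is 79.9% against 80.1%. If the table is used to draw 384 of 768, the split is met by construction. The split is not a reason for change.

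Finally, a reader might infer that ignoring hospital biases the result. With allocation truly random and concealed, it does not do so in expectation.

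**Conclusion.** The point holds in a limited form. For a single-blind trial at three hospitals, the documents name a random-number table and the order of events. They leave open who generates and holds the sequence, how it is concealed, and whether it is stratified by hospital. Nothing in them prevents foreknowledge of the next allocation; whether it would occur cannot be judged from them.

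The analyses carry no hospital term although site number is recorded. The resulting loss of precision is of unknown size. It is about 5% to 11% in the standard error if adjacent hospitals differ by 2 to 3 cycles, with an SD of 5 and equal hospital sizes, all of which are assumed. The false-positive rates under steering are likewise illustrations, not estimates for this trial.

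The change is worth making before enrolment: it is cheap, and concealment cannot be restored afterwards.

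**What to change.** **Protocol, Study design (Group A, Step 2) and Sampling Technique.** State that the list is generated centrally by someone not involved in enrolment, stratified by hospital, in permuted blocks of randomly varying size. State who holds it. Conceal it with sequentially numbered opaque envelopes or pre-coded bottles, opened only after consent and eligibility are recorded. If bottles are used, the arms must not be distinguishable from the outside. Block sizes should not be disclosed to the sites.

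**Protocol, Data Analysis, and SAP section 2.** Analyse the Group A comparison with a hospital term: a linear model with arm and hospital for Ct, and a Cochran-Mantel-Haenszel test by hospital for proportions.

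**Cost.** One list, a set of envelopes or coded bottles, a little logistics at three sites, and a line in the SAP. The hospital term uses two degrees of freedom (3 − 1) and a variable already collected. The trade-off is that blocks are somewhat more guessable than simple randomisation if staff recognise past allocations. Varying the block size limits this, and fixed small blocks should be avoided.

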#### 4. Mode of Action

The active moiety, non PVP- bound ('free') iodine is released into solution from the PVP- I complex. PVP itself has no microbicidal activity but rather delivers the free iodine to target cell membranes. It is this free iodine that mediates the basic mechanism of action (oxidation of amino acids and nucleic acids in biological structures), which is difficult, if not impossible, to counteract. This basic mechanism of action leads to strong microbicidal activity expressed by multiple modes of action that include the disruption of microbial metabolic pathways, as well as destabilisation of the structural components of cell membranes, causing irreversible damage to the pathogen. Consumed free iodine is then replaced by PVP- bound iodine. The concentration of free iodine is the determining factor of the microbicidal action of PVP- I. In a study investigating the virucidal activity of different disinfectants, electron micrographs revealed how exposure to iodine led to degeneration of surface proteins essential for the spread of enveloped viruses has also been noted. Furthermore, iodine is a scavanger of free radical oxygen species, contributing to anti-inflammatory properties. This interaction ultimately results in microbial death.

Corona virus is transmitted via respiratory droplets or aerosol, produced from sneezing or coughing of infected persons to healthy individual through mouth, nose and eye. After entry into nasopharynx and oropharynx and Eyes virus stayed there for certain period of time. Then it attached with ACE-2 receptor protein in nasopharynx and oropharynx and invade in to deeper cell s in to these areas. PONS containing 0.6 PVP-I will directly kill the virus and also keep the respective person protective layer of PVP-I for considerable time which will give an additional protection for individual user from SARS-CoV-2 virus infection.

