#### b. Secondary Objectives

- To assess the viral load in the nasopharynx and oropharynx before and after application of 0.6% PVP-I of participants of this study.
- To assess the duration of effectivity of 0.6% PVP-I on mucosal surface of participating COVID-19 patients by testing consecutive sample hourly upto 4hr.
- To estimate the shelf-life and stability of 0.6 % PONS.
- To characterize raw materials and impurities for product development and quality control/ assurance
- To measure the safety level of  $0.6\% \underline{PONS}$  by biochemical analysis of participants blood & urine

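### Group A swabs are taken 2-5 minutes after PVP-I with no stated iodine neutralisation or inhibition check, so part of any Ct difference could be an assay artefact confined to the PVP-I arm

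*Protocol*

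**What the plan says.** The protocol's Study design section gives the Group A sequence. The two arms receive different liquids: "Step 3: Application of 0.6% PVP-I spray to experimental group and distilled water to control group". A short wait follows: "Step 4: Follow up (waiting for 2-5 minutes" is the whole interval. Then comes the outcome sample: "Step 5: Collection of nasopharyngeal and oropharyngeal sawab for RT-PCR test for both group".

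Background section 4 (Mode of Action) says the product will "keep the respective person protective layer of PVP-I for considerable time". It also says that free iodine, once used up, is replenished from the PVP-bound store, and it gives the basic mechanism as "oxidation of amino acids and nucleic acids in biological structures".

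The notes after Study design make Ct the measure of viral concentration and read a high Ct as little viral genetic material. The primary endpoint (virucidal efficacy) has no other stated measure. Group B serves a secondary objective: "To assess the duration of effectivity of 0.6% PVP-I on mucosal surface of participating COVID-19 patients by testing consecutive sample hourly upto 4hr". No control arm is described for Group B.

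Neither the protocol nor the SAP names a neutraliser, rinse, transport medium, extraction method, internal control or inhibition check. The laboratory tests listed under raw materials and stability concern the product, not the swab assay.

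**The concern.** RT-PCR measures nucleic acid and relies on enzymes, which are made of amino acids. These are the two targets that the protocol gives for iodine. If a swab brings PVP-I into the tube, iodine could go on degrading viral RNA there, or impair the reaction. The reading would then no longer describe what was on the mucosa when the sample was taken.

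The usual safeguards do not deal with this. Randomisation balances the patients, not what is on the swab. Distilled water carries no iodine, so the control arm does not share the problem. A pre-spray sample, which the secondary objectives imply, would be iodine-free as well. More patients would only estimate a biased difference more precisely. At stake is whether a higher Ct in the PVP-I arm can be attributed to an effect in the nose and throat. The Group B samples used to judge duration could be affected in the same way.

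**Working it through.** **The plan's own figure.** Sample Size (protocol and SAP): n = Z²pq/d² = 1.96² × 0.5 × 0.5 / 0.05² = 384.16, so 384 per arm and 768 in Group A. This reproduces. It is a precision calculation for one proportion. It contains no Ct difference, SD or power, so it says nothing about how small a Ct shift the trial would declare significant.

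**Inputs.** From the documents: 384 per arm and 95% confidence (Z = 1.96). Assumed, because the documents give none of them: 100% PCR efficiency, a Ct SD of 5 cycles (range 4-6), a two-sample comparison of mean Ct, and the fraction of signal lost after sampling. The true effect is set to zero, so any significant result is pure artefact.

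**Step 1: signal loss to Ct delay.** Delay = -log2(1 - fraction lost).
- 10% lost: 0.15 cycles
- 30% lost: 0.51 cycles
- 50% lost: 1.00 cycle
- 90% lost: 3.32 cycles

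**Step 2: standard error of the arm difference.** SE = SD × √(2/384). For SD 4, 5 and 6 this is 0.289, 0.361 and 0.433. At SD 5, the smallest observed difference that reaches p < 0.05 is 1.96 × 0.361 = 0.71 cycles.

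**Step 3: probability of a significant result.** P = Φ(delay/SE - 1.96) + Φ(-delay/SE - 1.96).

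| Signal lost | SD 4 | SD 5 | SD 6 |
|---|---|---|---|
| 10% | 0.08 | 0.07 | 0.06 |
| 30% | 0.43 | 0.30 | 0.22 |
| 50% | 0.93 | 0.79 | 0.64 |
| 90% | near 1 | near 1 | near 1 |

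**Step 4: if results are read as positive or negative instead.** Suppose iodine turns 5% of otherwise positive PVP-I samples negative. With 5% background negatives, the arms have 0.05 + 0.95 × 0.05 = 9.75% and 5% negatives, and the difference is significant with probability 0.71. With 1% or 10% background negatives the probability is 0.96 or 0.48. These rates are also assumptions.

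**Direction.** By the protocol's mechanism, iodine in the tube or reaction can only remove RNA or impair enzymes. Both raise Ct or give a false negative, and both would be read as less virus in the PVP-I arm.

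**The case against.** The strongest reply is that only the omission is documented. Mode of Action describes iodine on target membranes and mucosa. It says nothing about transfer on a swab, dilution in the tube, survival through extraction or enzyme interference. The protocol gives no assay detail at all, so a laboratory procedure or an annexure not supplied here may cover the point, and the Ethical Issues section commits the study to Good Laboratory Practice. This stands as a limit on confidence. It does not close the gap, since a general commitment to good practice names neither a neutraliser nor an inhibition control.

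A reader might also infer more than the documents support:
- **That a false positive is likely.** The 0.79 is one row of an assumed range that runs from close to the nominal 5% to near certainty. It also presumes a comparison of mean Ct, whereas the Data Analysis section and the SAP only list tests.
- **That the trial's total error always favours PONS.** The direction holds for this artefact only. RT-PCR also counts RNA from killed virus, which could hide a real virucidal effect and work against PONS. The net direction is unknown.
- **That a fading Group B curve would be an artefact.** No passage gives the decay of residue, and a real, waning effect would look the same.

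**Conclusion.** The concern holds as an unaddressed possibility. By the protocol's own account, the sampled mucosa still carries active PVP-I, in one arm only, and nothing in either document stops the reaction at sampling or checks for inhibition. Part of a Ct difference in Group A could therefore be an assay artefact, and the Group B samples are open to the same doubt. Whether carry-over happens, and how much signal it removes, cannot be learned from the documents. On the assumptions above (SD 5, no true effect), the chance that such an artefact alone reaches significance goes from about 0.07 at 10% loss to nearly 1 at 90%. This should be fixed, with medium confidence. It can be settled at the bench before enrolment, whereas samples already collected without a neutraliser cannot be repaired.

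**What to change.** 1. **Neutralise at collection.** In Group A Step 5 and Group B Step 2, put every swab, in both Group A arms, into transport medium containing an iodine neutraliser such as sodium thiosulfate.
2. **Check before enrolment.** Spike replicate known-positive samples with PONS and measure the Ct shift with and without neutraliser. Require the shift to lie within a prespecified tolerance, for example 0.5 cycle. A 0.5-cycle shift corresponds to a loss of about 29% (1 - 2^-0.5), so by the table above a tighter limit may be preferred.
3. **Use an internal control.** Have it present in the collection medium, or at the latest added before extraction. A control added only at the PCR step cannot show RNA lost earlier in the tube. Re-run at dilution any sample whose control is delayed beyond a prespecified limit.
4. **Report control Ct by arm against a prespecified margin, not a significance test.** With an assumed control SD of 0.5 cycle, SE = 0.5 × √(2/384) = 0.036, so a trivial 0.1-cycle difference would be significant about 79% of the time. If the margin is exceeded, report the Ct difference as not attributable to PONS alone.

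The cost is a medium additive, one bench check, an internal control and some repeat PCR runs, with no extra patients, visits or swabs. The exact outlay depends on the assay platform, which the documents do not name. The observed effect may turn out smaller.
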